1.2. Potential Risks and Benefits

1.2.1. Potential Risks

General risks for intravitreal injection include infection, hemorrhage; precipitated angle closures; elevated intraocular pressure (IOP) with perfusion compromise; wound leak and hypotony; anaphylactic reaction to either the agent or periprocedural materials.

In addition, known risks associated with use of intravitreal methotrexate include:

- keratopathy. Therefore, all subjects will be recommended to use lubricating eye drops at a minimum of four times a day during the study period.

- mild conjunctival hyperemia (“red eye”) and slight pain at injection site. This hyperemia and/or slight pain is seen in almost all eyes receiving methotrexate and resolves within several hours.

1.2.2. Potential Benefit

Taking part in the clinical trial may or may not improve the subject’s vision. However, information learned from the clinical trial will help doctors understand more about how to improve vision in patients with retinitis pigmentosa.

2. CLINICAL TRIAL OBJECTIVE AND ENDPOINTS

2.1. Clinical Trial Objectives

To evaluate the safety and efficacy of repeated intravitreal ADX-2191 injections in subjects with retinal dystrophy (retinitis pigmentosa) with confirmed rhodopsin mutation (including P23H).

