
Overall Design: In this open-label Phase II clinical trial, 8 (eight) subjects with retinitis pigmentosa due to rhodopsin mutations (including P23H) will be identified and treated with serial intravitreal injections of ADX-2191 in the worse seeing eye. Ocular structure and function will be evaluated.
 
Retinitis pigmentosa (RP) is an inherited retinal disease that leads to a progressive degeneration of photoreceptors. Mutations within the rhodopsin gene account for approximately 25% of autosomal dominantly inherited RP cases. The mutation P23H (Substitution of Proline to Histidine at Codon 23 of the rhodopsin protein) is the most common mutation in the rhodopsin protein gene. The P23H mutation is associated with misfolded rhodopsin, which causes endoplasmic reticulum overload, activates the unfolded protein response and triggers apoptosis. Intravitreal methotrexate has been demonstrated in pre-clinical models of retinitis pigmentosa to promote clearance of misfolded rhodopsin without an effect on wild type rhodopsin protein and improves electroretinogram (ERG) responses in P23H mutant rodents. (Liu et al. (2020). Pharmacological clearance of misfolded rhodopsin for the treatment of RHO-associated retinitis pigmentosa. The FASEB Journal, 34(8), 10146–10167.)
 
ADX-2191 is an intravitreal formulation of the active drug substance commonly known as methotrexate. The drug substance is formulated at a concentration of 400 µg/0.05 ml in a sterile, aqueous buffered solution designed for intravitreal delivery. The drug product is supplied in single-dose, 2 mL glass vials with a 0.5 mL fill volume.
 
In this open label study, the first four subjects (Cohort A) will be treated with monthly intravitreal injections of ADX-2191 for a total of three injections; the last four subjects (Cohort B) will be treated with twice monthly intravitreal injections of ADX-2191 for a total of six injections. All subjects will be followed for a total of 16 weeks following dosing.
 
Clinical trial procedures to be conducted are outlined in the Schedule of Assessments (Table 1).
		
Study Objective: To evaluate the safety and tolerability of ADX-2191 in patients with retinitis pigmentosa due to confirmed rhodopsin mutations, including P23H.		
Primary endpoint: The primary endpoints of this study are safety and tolerability.		

Secondary endpoint: The secondary endpoints include:

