1. INTRODUCTION

1.1. Background and Therapeutic Rationale

Retinitis pigmentosa (RP) is an inherited retinal disease that leads to a progressive degeneration of photoreceptors. Mutations within the rhodopsin gene account for approximately 25% of autosomal dominantly inherited RP cases. The mutation P23H (Substitution of Proline to Histidine at Codon 23 of the rhodopsin protein) is the most common mutation in the rhodopsin protein gene. The P23H mutation is associated with misfolded rhodopsin, which causes endoplasmic reticulum overload, activates the unfolded protein response and triggers apoptosis. Intravitreal methotrexate has been demonstrated in pre-clinical models of retinitis pigmentosa to promote clearance of misfolded rhodopsin without an adverse effect on wild type rhodopsin protein and improves electroretinogram (ERG) responses in P23H mutant rodents. (*Liu et al. (2020). Pharmacological clearance of misfolded rhodopsin for the treatment of RHO-associated retinitis pigmentosa. The FASEB Journal, 34(8), 10146–10167.*)

The clinical pharmacology of ADX-2191 (intravitreal methotrexate) is based on inhibition of dihydrofolic acid reductase. Dihydrofolates must be reduced to tetrahydrofolates before they can be utilized in the synthesis of purine nucleotides and thymidylate. Therefore, methotrexate interferes with deoxyribonucleic acid (DNA) synthesis, repair, and cellular replication. Actively proliferating tissues such as malignant cells, bone marrow, fetal cells, buccal, intestinal mucosa, and cells of the urinary bladder are in general more sensitive to this effect of methotrexate. When cellular proliferation in malignant tissues is greater than in most normal tissues, methotrexate may impair malignant growth without irreversible damage to normal tissues.

Intravitreal injection provides the clinician with a means to bypass the blood retinal barrier and provide more therapeutic doses of the methotrexate to the affected tissues than could otherwise be achieved through oral or systemic dosing.

Aldeyra is proposing to conduct an open-label Phase II clinical trial in subjects with retinitis pigmentosa due to rhodopsin mutations (including P23H) whom will be treated with serial intravitreal injections of ADX-2191 (methotrexate 0.8%) in the worse seeing eye.

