2.2. Clinical Trial Endpoints

2.2.1. Primary Endpoints

The primary endpoint is safety and tolerability of ADX-2191.

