3. INVESTIGATIONAL PLAN

3.1. Overall Clinical Trial Design and Plan

In this open-label, non-comparator Phase II clinical trial, 8 (eight) evaluable subjects with retinitis pigmentosa due to rhodopsin mutations (including P23H) will be identified and treated with serial intravitreal injections of ADX-2191 in the worse seeing eye (“**the study eye**”). Ocular structure and function will be evaluated.

The first four subjects (Cohort A) will be treated with monthly intravitreal injections of ADX-2191 for a total of three injections; the last four subjects (Cohort B) will be treated with twice monthly intravitreal injections of ADX-2191 for a total of six injections. All subjects will be followed for a total of 16 weeks following dosing.

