9.2.6. Secondary Endpoint Analyses

Secondary endpoints will be analyzed to evaluate for change from Screening Visit B (Visit 2) to the level at Week 16 (Visit 10). Change from Screening level will be the dependent variable. The secondary endpoints include letters of BCVA or LLVA, improvement in visual field area and microperimetry, and increase in dark-adapted flash b-wave amplitudes.

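### Section 2.1 sets an efficacy objective that the synopsis and primary endpoint do not share, and this uncontrolled 16-week design can describe change but not attribute it to the drug

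*Combined protocol and SAP*

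**What the plan says.** Section 2.1 gives the sole objective as "To evaluate the safety and efficacy of repeated intravitreal ADX-2191 injections" in subjects with a confirmed rhodopsin mutation. The synopsis reads "Study Objective: To evaluate the safety and tolerability of ADX-2191 in patients with retinitis pigmentosa due to confirmed rhodopsin mutations, including P23H". Section 2.2.1 agrees with the synopsis: "The primary endpoint is safety and tolerability of ADX-2191". In both the synopsis and Section 2.2.2, acuity, low-luminance acuity, microperimetry, ERG, dark-adapted perimetry and OCT are secondary endpoints.

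Section 3.1 describes the design: "In this open-label, non-comparator Phase II clinical trial, 8 (eight) evaluable subjects with retinitis pigmentosa". The first four subjects receive three monthly injections, and "the last four subjects (Cohort B) will be treated with twice monthly intravitreal injections of ADX-2191 for a total of six injections". Section 3.4 gives a duration of about 16 weeks. Section 1.1 calls the disease an "inherited retinal disease that leads to a progressive degeneration of photoreceptors" and gives no rate of decline.

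Section 9.2.6 analyses change from Screening Visit B (V2) to Week 16 (V10). It lists letters of BCVA or LLVA without a direction, then "improvement in visual field area and microperimetry, and increase in dark-adapted flash b-wave amplitudes". Section 9.2.1 sets two-sided analyses at the 0.05 level. Section 9.2.3 says that a single hypothesis will be tested, but does not name it.

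**The concern.** The two statements of the objective answer different questions. Section 2.1 drops tolerability and adds efficacy, and the primary endpoint does not address efficacy. No rule says which statement governs: Sections 9.2.1 and 9.2.8 give the SAP precedence on statistical procedures only.

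The difference matters because nothing in the design separates a drug effect from what would have happened anyway. Section 1.1 describes progressive loss and a drug meant to clear the misfolded protein that triggers cell death, so slower loss is one plausible benefit. It also cites improved ERG responses in mutant rodents, so improvement is another. Without a comparator or reference rate, stable function at Week 16 fits both disease arrest and the ordinary slow course. Improvement fits a drug effect, but also practice on perimetry and acuity charts, regression to the mean after choosing the worse-seeing eye, and expectation in subjects who know they are treated. If Section 2.1 stands, eight uncontrolled subjects could be reported as showing efficacy, or as refuting it because nothing improved. Neither conclusion would follow.

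**Working it through.** **1. The plan's own figure.** The stated size is eight evaluable subjects. No effect size, SD, power or reference rate is given, so the figure cannot be reproduced and there is no efficacy calculation to check.

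**2. What the design offers for attribution.**
- Concurrent control: none (Section 3.1).
- Randomised contrast: none. Both cohorts are active and are filled by order of entry.
- Historical or natural-history rate: none given.
- Fellow-eye contrast: not planned. BCVA, LLVA and ERG are bilateral, as is OCT at V1, V9 and V10. MAIA and DAC test the study eye only (Sections 6.7.1 to 6.7.6).
- Named efficacy hypothesis or success threshold: none.

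**3. Precision.** In units of the SD of change, the 95% half-width for a mean change is t(0.975, n−1)/√n:
- n = 8: 2.365/2.828 = 0.84 SD
- n = 4 (one cohort): 3.182/2 = 1.59 SD
- Cohort A minus Cohort B: t(0.975, 6) × √(1/4 + 1/4) = 2.447 × 0.707 = 1.73 SD

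The effects detectable with 80% power at two-sided 0.05 (noncentral t) are 1.16 SD at n = 8, 2.13 SD at n = 4 and 2.38 SD between cohorts.

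**4. Non-drug shift.** Suppose that the drug does nothing but practice, regression to the mean or expectation moves the mean by b SD. The sizes of b are assumptions. The chance of a nominally significant improvement at n = 8 is P(T > 2.365), where T is noncentral t with 7 degrees of freedom and noncentrality b√8:

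| Assumed shift b (SD) | Chance of a significant improvement |
|---|---|
| 0.25 | 9% |
| 0.50 | 23% |
| 0.75 | 45% |
| 1.00 | 68% |

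The chance rises with b, and for a given shift more subjects would raise it further. The missing element is a comparison, not only precision.

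**5. Several secondary tests.** If the six secondary domains were each tested at 0.05 and were independent (an assumption), the chance of at least one false positive would be 1 − 0.95⁶ = 26.5%.

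**6. Slowed loss, as illustration only.** The observation period is 16/52 = 0.308 year. Under an assumed untreated loss of 5% to 10% a year, 16 weeks covers 5% × 0.308 = 1.5% to 10% × 0.308 = 3.1%. With compounding, 1 − (1 − r)^0.308, over an assumed 1% to 15% a year, the range is 0.3% to 4.9%. That is all that complete arrest could save in the period. No measurement SD is given, so these percentages cannot be set against the half-widths in step 3.

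**The case against.** *Evaluating efficacy is not the same as concluding on it.* Safety and tolerability are primary in both places, every visual measure is secondary, and no success criterion exists. A signal-seeking Phase II study in eight subjects is a legitimate choice. This stands: the descriptive data are worth having, and an intention to claim efficacy cannot be inferred. The conflict between the two objectives remains.

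*Section 2.1 may be the fuller statement.* The synopsis lists six secondary endpoints that its own objective does not cover. This also stands, and it is why the repair should add a matching secondary objective in both places instead of only deleting a word.

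*The plan has mitigating features.* Much of the testing is bilateral, BCVA technicians are masked, and BCVA, LLVA, MAIA and DAC are each run twice before dosing. These may limit assessor bias and early learning. They do not supply a comparator: no fellow-eye contrast is planned, and the treated eye is chosen as the worse one. Section 11.7 mentions a control cohort, but the design contains none.

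*Section 9.2.6 looks only for improvement.* A reader might infer this from the words quoted from it, but the text does not support it. The section opens with change, makes change the dependent variable and gives BCVA and LLVA no direction, and Section 9.2.1 is two-sided. What is true is narrower: the visual field, microperimetry and ERG outcomes are worded as gains.

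*The separate SAP may settle the framing.* Section 9.2.8 defers detail to an SAP to be finalised before database lock. Its text is not among the documents available, so the protocol must be judged as it reads.

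**Conclusion.** The point holds in a limited form. The two current statements of the objective conflict, and the design cannot support a conclusion for or against efficacy. It can support description of safety, tolerability and observed change. The defect lies in the objective and in the claims that could be drawn from it; the primary endpoint is consistent throughout and no data collection is affected. It should be corrected, but it does not block the trial.

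The half-widths of 0.84 SD and 1.59 SD follow from the stated numbers of subjects and the usual t assumptions. The 9% to 68% range rests on assumed non-drug shifts. A reader might take the 1.5% to 3.1% loss as a property of this population or as a ceiling on benefit. The documents do not support that: they give no progression rate, and the figure concerns arrest only, not improvement. The attribution argument does not depend on it.

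**What to change.** - **Section 2.1 and synopsis:** use the same text in both. Primary objective: safety and tolerability. Secondary objective: *to describe change in visual function and retinal structure by cohort*. Keep the existing secondary endpoints under that label.
- **Section 9.2.6:** state that these analyses are descriptive (estimates with 95% confidence intervals, in either direction) and that change, or its absence, will not be reported as confirmatory evidence for or against efficacy. Use direction-neutral wording for visual field, microperimetry and ERG. Cover every secondary endpoint at its own last assessment. ERG is collected only at V1 and V9 (Section 6.7.4), so the V2-to-V10 change does not exist for it. OCT also has no V2 scan and needs V1 as its baseline.
- **Sections 9.2.1 and 9.2.3:** remove the single hypothesis or name it, so that no secondary p-value is read as an efficacy test. Carry the same framing into the SAP.

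If the sponsor prefers to keep efficacy as an objective, it would have to prespecify a comparator or reference rate, an estimand, one named hypothesis and a duration justified by a stated progression rate.

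The recommended cost is wording in the synopsis, these sections and the SAP, with no change to visits, subject numbers or clinical management. The downside is a less ambitious stated objective.

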2.2. Clinical Trial Endpoints

2.2.1. Primary Endpoints

The primary endpoint is safety and tolerability of ADX-2191.

2.2.2. Secondary Endpoints

The secondary endpoint include:

- 1) Best Corrected Visual Acuity (BCVA): Change in BCVA will be assessed using a normally illuminated ETDRS (Early Treatment Diabetic Retinopathy) chart.
- 2) Low-luminance visual acuity (LLVA): Change in Low-luminance visual acuity (LLVA) and the low luminance deficit (LLD) will be assessed. The LLD is defined as the difference between the BCVA and LLVA. LLVA will be assessed using a 2.0 log unit neutral density filter while reading a normally illuminated ETDRS (Early Treatment Diabetic Retinopathy) chart.
- 3) Macular Integrity Assessment (MAIA) Microperimetry: Central retinal sensitivity will be assessed using MAIA microperimetry using a standard 10-2 test grid with a Goldman size III stimulus of various intensities presented on a mesopic background (4 apostilbs).
- 4) Full field Electroretinography (ffERG): Change in dark-adapted flash ($0.01 \text{ cd} \cdot \text{s} \cdot \text{m}^{-2}$) b-wave amplitudes will be analyzed. Testing will be performed using a standard International Society for Clinical Electrophysiology of Vision (ISCEV) protocol.
- 5) Dark-Adapted Chromatic Perimetry: Change in dark adapted retinal sensitivity (dB) to the blue and red stimuli on the Medmont Dark-Adapted Chromatic (DAC) perimeter will be assessed.
- 6) OCT: Change in Central Subfield Foveal Thickness (CSFT) and Change in Ellipsoid Zone (EZ) area/width will be assessed using a spectral domain optical coherence tomograph (SD-OCT) volume scan using the Heidelberg Spectralis.

3. INVESTIGATIONAL PLAN

3.1. Overall Clinical Trial Design and Plan

In this open-label, non-comparator Phase II clinical trial, 8 (eight) evaluable subjects with retinitis pigmentosa due to rhodopsin mutations (including P23H) will be identified and treated with serial intravitreal injections of ADX-2191 in the worse seeing eye (“**the study eye**”). Ocular structure and function will be evaluated.

The first four subjects (Cohort A) will be treated with monthly intravitreal injections of ADX-2191 for a total of three injections; the last four subjects (Cohort B) will be treated with twice monthly intravitreal injections of ADX-2191 for a total of six injections. All subjects will be followed for a total of 16 weeks following dosing.

3.2. Subject Numbering

Each subject screened for the clinical trial will be assigned a unique subject number that will be used to identify the subject throughout subject participation in the clinical trial.

3.3. Safety Oversight

During the clinical trial, subject safety will be monitored on a continuous basis by the Sponsor Medical Monitor until the last subject completes the last scheduled clinical trial assessment.

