Assessment	Visit 1 (V1)	Visit 2 (V2)	Visit 3 (V3)	Visit 4 (V4)	Visit 5 (V5)	Visit 6 (V6)	Visit 7 (V7)	Visit 8 (V8)	Visit 9 (V9)	Visit 10 (V10)
	Screening Visit A	Screening Visit B Week 0	Day 4 ¹	Week 2 ²	Week 4 ²	Week 6 ³	Week 8 ³	Week 10 ³	Week 12 ³	Week 16 ³
Informed consent	X									
Eligibility criteria	X									
Demography, medical and ocular history	X									
Best Corrected Visual Acuity	X ⁴	X ^{4,6}	X ⁴		X ⁴		X ⁴		X ⁴	X ⁴
Low Luminance Visual Acuity	X ⁴	X ^{4,6}	X ⁴		X ⁴		X ⁴		X ⁴	X ⁴
Full ophthalmic exam, including intraocular pressure, slit lamp, and dilated funduscopy	X ⁴		X ⁴		X ⁴		X ⁴		X ⁴	X ⁴
Wide-field Color Fundus Photography and Autofluorescence	X ⁴								X ⁴	X ⁴
Macular SD-OCT (Spectral Domain Optical Coherence Tomography)	X ⁴				X ⁷		X ⁷		X ⁴	X ⁴
Dark-Adapted Chromatic (DAC) Perimetry	X ⁷	X ^{6,7}	X ⁷		X ⁷		X ⁷		X ⁷	X ⁷
Macular Integrity Assessment (MAIA) Microperimetry	X ⁷	X ^{6,7}	X ⁷		X ⁷		X ⁷		X ⁷	X ⁷
Full field electroretinography	X ⁴								X ⁴	
Cohort A (Monthly ADX-2191 injection)										
Corneal Slit Lamp Safety Exam		X ⁷								
Urine Pregnancy Test		X			X		X			
Intravitreal injection of ADX-2191		X ^{5,7}			X ^{5,7}		X ^{5,7}			
Concomitant medications	X	X	X		X		X		X	X
Adverse events	X	X	X		X		X		X	X
Cohort B (Bimonthly ADX-2191 injection)										
Corneal Slit Lamp Safety Exam		X ⁷		X ⁷		X ⁷		X ⁷		
Urine Pregnancy Test		X		X	X	X	X	X		
Intravitreal injection of ADX-2191		X ^{5,7}		X ^{5,7}	X ^{5,7}	X ^{5,7}	X ^{5,7}	X ^{5,7}		
Concomitant medications	X	X	X	X	X	X	X	X	X	X
Adverse events	X	X	X	X	X	X	X	X	X	X

¹: Visit window +/- two days²: Visit window +/- three days³: Visit window +/- five days⁴: Bilateral evaluation⁵: Injection to be performed after all other assessments have been performed.⁶: Results from Screening Visit B (V2) will be used for quantitative study analysis purposes.

Investigator may repeat any tests of Screening Visit B on a separate unscheduled visit if a difference in results is observed from Screening Visit A, as per investigator assessment

⁷: Study eye only

TABLE OF CONTENTS

INVESTIGATOR STATEMENT2

SUMMARY OF CHANGES3

SYNOPSIS4

LIST OF ABBREVIATIONS AND DEFINITION OF TERMS12

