5.1. Description of Investigational Product

Methotrexate is an antimetabolite and antifolate drug that has been used for cancer treatment since the 1950s. The drug was originally approved in 1959 and is now available generically. It has exceptionally well-understood biological and clinical effects. Methotrexate is currently FDA-approved for oral administration and for intravenous, intramuscular, intrathecal, or intra-arterial injection. Approved indications include psoriasis, rheumatoid arthritis, and certain neoplastic diseases. Other mechanisms of action involve direct effects on inflammatory pathways, in particular neutralization of the effects of TNF- α and IL-1 β , though the molecular mechanisms underlying these effects remain largely uncharacterized.

Several case series have been published using intravitreal injections of methotrexate, most commonly for intraocular lymphoma. (Frenkel et al., 2008; Hardwig, Pulido, & Bakri, 2008; Hardwig, Pulido, Erie, Baratz, & Buettner, 2006; Samson, Waheed, Baltatzis, & Foster, 2001)

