6.5. Adverse Events

Any serious, unexpected adverse events (AE) believed to be due to the intervention rather than the natural disease process will prompt a filing of an adverse event form with the local IRB office and the FDA.

AEs will be collected from the time the subject signs the informed consent form through 30 days after the last dose of IP. AEs must be recorded in the CRF. The Sponsor and investigator or qualified site staff will review and evaluate AEs on an ongoing basis. See Section 8 for further detail on AE reporting.

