6.7.7. Full Ophthalmic Clinical Examination

Routine full ophthalmic, dilated exams, including intraocular pressure measurement, slit lamp examination, and dilated funduscopy will be performed on Screening Visit A (V1) and Visits V3, V5, V7, V9, V10. Both eyes will be examined at all time points. The full ophthalmic exam will also serve as the corneal safety assessment on days when a full ophthalmic exam is done prior to an intravitreal injection.

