8.6.2. Reporting Serious Adverse Events

The investigator is responsible for reporting all SAEs, regardless of causality, to the Sponsor designee within 24 hours of learning of the occurrence. The paper SAE form must be sent to the study Medical Monitor, [name], at [contact]

The reporting timeframe starts when the subject signs the informed consent or assent form through 30 days after the last IP administration. At a minimum, a description of the event and the Investigator’s judgment of causality must be provided at the time of the initial report. These preliminary reports will be followed by detailed descriptions that will include copies of hospital case reports, autopsy reports, and other documents when requested and applicable.

A follow-up SAE Report must be submitted within 24 hours of the investigator receiving the follow-up information (such as information regarding complications, progression or resolution).

An SAE that is considered completely unrelated to a previously reported event should be reported separately as a new SAE.

The original copy of the SAE Report Form and the fax confirmation sheet (or email) must be kept with the source documentation at the clinical trial site.

Follow-up information should be communicated the same way, using a new SAE Report Form stating that it is a follow-up to the previously reported SAE and giving the date of the original report. The follow-up information should describe whether the event has resolved or continues, if and how it was treated, and whether the subject continued or withdrew from clinical trial participation.

The investigator and qualified site staff should institute any supplemental investigations of SAEs based on their clinical judgment of likely causative factors. This may include clinical laboratory tests not specified in the protocol, histopathologic examinations, or consultations with specialists. The Sponsor or their designee may also request the investigator to conduct supplemental assessments.

If the SAE was not previously documented in the Investigator's Brochure and is thought to be related to IP, the Sponsor or their designee may urgently require further information from the investigator for regulatory authority reporting. The Sponsor may need to issue an investigator Notification to inform all investigators involved in any clinical trial with the same drug that this SAE has been reported.

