8.6.3. Follow-up of Adverse Events

All AEs will be followed until stabilization/resolution or until clinical database lock. AEs are to be reported to the IRB in accordance with IRB policy.

All SAEs will undergo active follow-up until resolved or the event becomes chronic or stable. Follow-up data for SAEs obtained after clinical database lock will be incorporated into the safety database.

8.6.4. Reporting Serious Adverse Events to Regulatory Health Authorities/ Institutional Review Boards/Research Ethics Boards/Independent Ethics Committees

The investigator is responsible for following all local regulations for the reporting of safety information, including the reporting of SAEs to their local IRB/REB/IEC.

The investigator must promptly report to his or her local IRB/REB/IEC all unanticipated problems involving risks to subjects. This includes death from any cause and all serious adverse events reasonably or possibly associated with the use of IP.

The Sponsor or their designee is responsible for appropriate reporting of relevant AEs, suspected unexpected serious adverse reactions (SUSARs) involving IP, to all regulatory authorities.

In addition, the Sponsor or designee will be responsible for the submission of safety letters (e.g., SUSARs) to the central IRB/REB/IEC and to participating investigators of all SUSARs involving IP according to applicable regulations.

After termination of the clinical trial (determined as last subject, last visit), any unexpected safety issue that changes the risk-benefit analysis and is likely to have an impact on the subjects

who have participated in it, will be reported by the Sponsor as soon as possible to the competent authority (ies) concerned together with proposed actions.

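### Cohort B doubles injection frequency and cumulative dose, but nothing requires Cohort A repeat-injection data to exist or be reviewed before Cohort B starts

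*Combined protocol and SAP*

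**What the plan says.** Protocol Section 3.1 fills the cohorts by order of entry. The first four subjects get three monthly injections; "the last four subjects (Cohort B) will be treated with twice monthly intravitreal injections of ADX-2191 for a total of six injections". Each injection is 400 µg in 0.05 mL in both cohorts (Section 5.4). Table 1 places Cohort A injections at Weeks 0, 4 and 8, and Cohort B injections at Weeks 0, 2, 4, 6, 8 and 10. A footnote to Table 1 reads "Injection to be performed after all other assessments have been performed". Full ophthalmic examinations "will be performed on Screening Visit A (V1) and Visits V3, V5, V7, V9, V10" (Section 6.7.7); Visits 4, 6 and 8 are for Cohort B only.

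The safeguards in the protocol are these:

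- **Oversight.** Under Section 3.3, "subject safety will be monitored on a continuous basis by the Sponsor Medical Monitor". Section 6.5 adds "The Sponsor and investigator or qualified site staff will review and evaluate AEs on an ongoing basis".
- **Reporting.** Section 8.6.2 makes the investigator responsible for "reporting all SAEs, regardless of causality, to the Sponsor designee within 24 hours of learning of the occurrence", with the form going to the Medical Monitor. Section 8.6 reads visual-threat SAEs broadly, to include any potential damage to the eyes. Section 8.6.4 adds "The investigator must promptly report to his or her local IRB/REB/IEC all unanticipated problems involving risks to subjects".
- **Individual subjects.** There is a corneal examination before every injection (Sections 6.7.7, 6.7.9, 6.10), lubricant is prescribed (6.9), and subjects are removed for endophthalmitis or loss of light perception (4.3).
- **Trial level.** The sponsor may discontinue the trial (11.13). No interim analysis is planned (9.2.7).

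None of these is tied to the opening of Cohort B.

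**The concern.** Treating the less intensive cohort first helps safety only if what is learned there can inform the step up. As written, subject 5 may start the twice-monthly schedule as soon as the four Cohort A places are filled, whatever Cohort A has or has not shown about repeat injections.

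The findings most exposed to this are the non-serious ones. Section 8.1 does not count an abnormal examination finding as an adverse event unless it is symptomatic, leads to stopping treatment or is judged clinically relevant. Section 11.9 uses paper case report forms that are entered after monitoring. Modest slit-lamp, pressure, acuity or fundus changes in Cohort A therefore need not be in front of the Medical Monitor when Cohort B begins. Cohort B's added visits at Weeks 2, 6 and 10 schedule a corneal examination but no acuity, pressure or dilated examination.

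**Working it through.** **1. Exposure (Section 3.1, Section 5.4, Table 1).** Counting injection visits reproduces the plan's 3 and 6.

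- Cohort A: 3 × 400 = 1,200 µg per study eye, every 4 weeks.
- Cohort B: 6 × 400 = 2,400 µg, every 2 weeks. The ratio is 2.0 for both frequency and total.
- The Week 0 injection is the same in both cohorts. The schedules first differ at Week 2.
- Cohort B has had 3 × 400 = 1,200 µg at Week 4, equal to Cohort A's total, and 4 × 400 = 1,600 µg at Week 6, where it first exceeds it.

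**2. When Cohort A can first show a repeat-injection finding.** The second Cohort A injection is at Week 4, after that day's assessments. Cohort A has no visit at Week 6. Week 8 (Visit 7) is therefore its first scheduled examination after a repeat injection. That examination precedes the third injection, so it is sure to reflect only 2 × 400 = 800 µg: 800/1,200 = 67% of the Cohort A total and 800/2,400 = 33% of the Cohort B total.

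**3. How many Cohort A subjects have reached Week 8.** The protocol gives no accrual rate, so assume even spacing of *d* weeks. Subject 5 is due at 4*d*. When subject 5 is at week *w*, the Cohort A subjects stand at 4*d*+*w*, 3*d*+*w*, 2*d*+*w* and *d*+*w* weeks. Count those at or past 8.0 weeks; in brackets, those at or past 8 weeks + 5 days = 8.71 weeks, the late edge of the Visit 7 window.

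| Subject 5 at | d = 1 | d = 2 | d = 4 | d = 8 |
|---|---|---|---|---|
| Week 0 (same injection in both cohorts) | 0 (0) | 1 (0) | 3 (2) | 4 (3) |
| Week 2 (schedules diverge) | 0 (0) | 2 (1) | 3 (3) | 4 (4) |
| Week 6 (B first exceeds A's total) | 3 (2) | 4 (3) | 4 (4) | 4 (4) |

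Example: *d* = 2, *w* = 2 gives 10, 8, 6 and 4 weeks, so two subjects have nominally reached Week 8.

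**4. What four subjects could show.** With per-subject risk *p* over the full Cohort A course and a share *f* of events visible by Week 8 (both assumed), P(at least one event in four) = 1 − (1 − *fp*)⁴.

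| p | 5% | 10% | 20% | 30% | 50% |
|---|---|---|---|---|---|
| f = 1 | 19% | 34% | 59% | 76% | 94% |
| f = 1/2 | 10% | 19% | 34% | 48% | 68% |

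These figures say what Cohort A might reveal. They do not measure the added benefit of a review. With 0 events in 4, the one-sided 95% upper limit is 1 − 0.05^(1/4) = 53%.

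**5. Delay if Cohort B waits.** Subject 4 reaches Visit 7 at 3*d* + 8, and subject 5 is due at 4*d*, so the delay is max(0, 8 − *d*): 7, 6, 4 or 0 weeks for *d* = 1, 2, 4, 8. With a late Visit 7 it is 8.71 − *d*: 7.7, 6.7, 4.7 or 0.7 weeks.

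**The case against.** The best case for leaving the text alone has four parts.

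- **The exposure gap is narrower than a count at subject 5's first injection suggests.** That injection is identical in both cohorts. By the time a Cohort B eye exceeds Cohort A's total, three or four Cohort A subjects have nominally reached Week 8 even at 1- to 2-week spacing. This stands, and it limits the gap to the early Cohort B injections under fast accrual.
- **Existing safeguards cover the gravest events.** Vision-threatening events go to the Medical Monitor within 24 hours of the investigator learning of them. Keratopathy, the principal drug-specific risk in Section 1.2.1, is looked for before each injection. This also stands. It does not reach the non-serious findings described above, and the corneal check acts on one subject at a time.
- **A review of four subjects is weak evidence.** It may see only two injections given four weeks apart, cannot test a two-week interval, and leaves a 53% upper limit after no events. That is correct. The review is procedural, and events already seen would be reported without it.
- **The sponsor may already have grounds to proceed.** Section 5.1 notes "Several case series have been published using intravitreal injections of methotrexate, most commonly for intraocular lymphoma", and Section 8.4 refers to an Investigator's Brochure. Whether either supports twice-monthly dosing cannot be judged from these documents, nor whether a step-up decision is recorded elsewhere.

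A reader might infer that this is an uncontrolled dose escalation, or that Cohort B is unprotected. The documents support neither: the protocol does not call the design dose escalation, the dose per injection is constant, and several safeguards operate throughout.

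**Conclusion.** The point holds as a minor, inexpensive safety improvement. Frequency and cumulative dose double, and no provision makes the start of Cohort B depend on Cohort A repeat-injection data. The open part is non-serious or cumulative findings when accrual is fast: at 1- to 2-week spacing, none to two of the four Cohort A subjects have nominally reached Week 8 when the schedules diverge. At about 8-week spacing the gap closes by itself. These counts rest on assumed even accrual, and the event probabilities rest on assumed risks. A reader might take the omission to undermine the trial's results; it does not, because no endpoint, estimate or analysis is affected.

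**What to change.** In Section 3.3, cross-referenced in 3.1, state that Cohort B dosing does not begin until both conditions are met:

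1. Each of the first four treated Cohort A subjects has completed Visit 7 (Week 8), has passed the end of the Visit 7 window without attending, or has discontinued.
2. The existing Sponsor Medical Monitor has documented a review of accumulated Cohort A adverse event, slit-lamp, ophthalmoscopy, intraocular pressure and BCVA data, with a decision to proceed, modify or stop.

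Add that replacement subjects enrolled under Section 4.4 do not restart the wait, and note in 9.2.7 that this is a safety review and not an interim efficacy analysis. Holding before the first Cohort B injection, although it is identical to Cohort A's, avoids starting a subject whose second injection might then miss its ±3-day window. No numeric stopping threshold is proposed, because four subjects cannot support one. Cohort A events after Week 8 stay under the existing continuous monitoring.

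The cost is a few sentences and one documented review by existing staff of data already scheduled, with no added patients, procedures or committee. The real price is a delay to Cohort B of about 0 to 7.7 weeks over the spacings considered, longest when accrual is fastest, plus review time.
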